#### 19.3 Independent Data Monitoring Committee

An IDMC will be instigated to monitor the progress of the trial. Membership of the IDMC will be proposed by the TMG and approved by the TSC. The Committee's terms of reference, roles and responsibilities will be defined in a charter issued by ICR-CTSU and based on MRC GCP. The IDMC should meet in confidence at regular intervals, and at least annually. A report of the findings and recommendations will be produced following each meeting and a summary of the minutes will be submitted to the TMG and TSC, and if required, the main REC.

The IDMC reserve the right to release any data on outcome or side-effects through the TSC to the TMG (and if appropriate to participants) if it determines at any stage that the combined evidence from this and other studies justifies it.

#### 20. RESEARCH GOVERNANCE

#### 20.1 Sponsor Responsibilities

The Institute of Cancer Research (ICR) is the agreed Sponsor of this study in accordance with the Research Governance Framework for Health and Social Care and the principles of Good Clinical Practice (GCP).

#### The following responsibilities have been delegated to:

#### The Chief Investigator:

- selection of Investigators
- taking appropriate urgent safety measures

The Chief Investigator or a named deputy delegated in his absence:

 prompt decision as to which related adverse events are related unexpected SAEs and prompt reporting of that decision to ICR-CTSU for onward reporting to the main REC

## The Institute of Cancer Research (ICR-CTSU)

ICR-CTSU has overall responsibility for facilitating and coordinating the conduct of the trial and is also responsible for collating data obtained, and undertaking and reporting interim and final analyses.

The responsibilities of ICR-CTSU for the day-to-day management of the trial will include the following.

- ensuring an appropriate ethics opinion has been sought, and any amendments have been approved
- giving notice of amendments to protocol, make representations about amendments to the Main REC
- giving notice that the trial has ended
- randomising patients
- raising and resolving queries with local investigators
- issuing and collating QL questionnaires returned by post
- logging clinical and QL data received; raising queries
- keeping records of all serious adverse events (SAEs) reported by investigators
- notifying the Main REC and Investigators of related Serious Adverse Events

## The Participating Centres

- putting and keeping in place arrangements to adhere to the principles of GCP
- keeping a copy of all 'essential documents' (as defined under the principles of GCP) and ensuring appropriate archiving and destruction of documentation once the trial has ended
- taking appropriate urgent safety measures

Centres wishing to recruit to this study will be asked to provide evidence that they can deliver protocol treatment. This will include the successful completion of the FAST-Forward QA programme (see Appendix 3).

Responsibilities are defined in an agreement between an individual participating centre and The Institute of Cancer Research, which must be signed and in place before recruitment can commence.

# 21. TRIAL ADMINISTRATION AND LOGISTICS

## 21.1 Protocol Compliance

The FAST-Forward trial is being conducted in accordance with the professional and regulatory standards required for non-commercial research in the NHS under the Research Governance Framework for Health and Social Care and the principles of GCP. Before activating the trial, participating centres are required to sign an agreement between an individual participating centre and The Institute of Cancer Research. Centres may commence recruitment once centre agreements have been signed by both parties, trial documentation is in place and a site initiation (visit or teleconference) has taken place. Site initiation visits will be conducted at centres where the Principal Investigator has requested one or where ICR-CTSU deems it is appropriate.

#### 21.2 Protocol Amendments

Proposed protocol amendments will be submitted to the TMG by the Chief Investigator. The TMG will agree protocol amendments prior to acceptance and submission to the Main REC. Once approved the Principal Investigator at each centre will be informed of the change and sent all the associated documentation. It is the Principal Investigator's responsibility to submit amendments to their R&D department for approval. Confirmation that this has been done must be provided to ICR-CTSU.

## 21.3 Investigator Training

Training and advice will be provided via a trial launch meeting, training workshops, site initiation and QA feedback to identified key individuals in each participating centre by members of the Trial Management Group. Participating centres will be asked to maintain a screening log to monitor randomisation acceptance rates, and additional support/training will be offered when lower than anticipated rates are encountered.

## 21.4 Data Acquisition

The clinical data should be recorded on the FAST-Forward case report forms (CRFs) and the relevant pages forwarded to ICR-CTSU in a timely manner. The Trial Management Group reserves the right to amend or add to the CRFs as appropriate. Such changes do not constitute a protocol amendment, and revised or additional forms should be used by centres in accordance with the guidelines provided by ICR-CTSU. Where appropriate, data may need to be collected retrospectively if an additional question has been added to the CRF.

By participating in the FAST-Forward trial, the Principal Investigators at each centre are confirming agreement with his/her local NHS Trust to ensure that

- sufficient data is recorded for all participating patients to enable accurate linkage between hospital records and CRFs
- source data and all trial related documentation are accurate, complete, maintained and accessible for monitoring and audit visits
- original consent forms are dated and signed by both patient and investigator and are kept together in a central log together with a copy of the specific patient information sheet(s) given at the time of consent
- all essential documents must be retained after the trial ends to comply with current legislation
- staff will comply with the protocol and Trial Guidance Notes for FAST-Forward

On receipt at ICR-CTSU, CRFs will be recorded as received and any missing forms will be reported to the originating centre. Illegible forms may be returned to the centre for clarification.

## 21.5 Central Data Monitoring

ICR-CTSU will review incoming CRFs for compliance with the protocol, and for inconsistent or missing data. Should any missing data or data anomalies be found, queries will be sent to the relevant centre for resolution. Following initial review, the CRF data items will be entered into the clinical study database held at ICR-CTSU.

Data will be further reviewed for data anomalies / missing data, by central statistical monitoring. Any systematic inconsistencies identified may trigger monitoring visits to centres.

## 21.6 On site Monitoring

If a monitoring visit is required, ICR-CTSU will contact the centre to discuss dates of proposed visit. Once a date has been confirmed, the centre should ensure that the relevant patient notes are available for monitoring.

If any problems are detected in the course of the monitoring visit, ICR-CTSU will work with the Principal Investigator to resolve issues and, if necessary, to determine the centre's future participation in the study.

ICR-CTSU staff conducting on-site monitoring will review essential documentation and carry out source data verification to confirm compliance with the centre agreement and trial protocol to ensure the protection of patients' rights as detailed in the Declaration of Helsinki 1964 as amended October 1996.

## 21.7 End of Study

The study end date is deemed to be the date of the last data capture and is expected to be at least 10 years after the last patient is entered.

# 21.8 Archiving

Essential documents are documents that individually and collectively permit evaluation of the conduct of the trial and substantiate the quality of the data collected. Essential documents will be maintained at ICR-CTSU in a way that will facilitate the management of the trial, audit and inspection. They should be retained for a sufficient period (at least 15 years) for possible audit. Documents should be securely stored and access restricted to authorised personnel.

Essential documents should also be archived at each participating centre in accordance with current legislation.

## 22. PATIENT PROTECTION AND ETHICAL CONSIDERATIONS

#### 22.1 Risk Assessment

This study has been formally assessed for clinical risk using the ICR-CTSU risk assessment tool.

# 22.2 Patient Confidentiality

Patients will be asked to consent to their full name being collected at randomisation in addition to their date of birth, hospital number, postcode and NHS number (CHI in Scotland). This will allow tracing through the GP and national records to assist with long term follow up and to permit linkage with routinely collected NHS data. The personal data recorded on all documents will be regarded as confidential, and any information which would allow individual patients to be identified will not be released into the public domain.

Patients consenting to the Quality of Life study will provide their name, address and telephone number and also address and phone number of their GP to ICR-CTSU.

These details will only be used for the purposes of the Quality of Life study. The principal investigator must keep a separate log of patients' trial numbers, names, and hospital numbers. The principal investigator must maintain in strict confidence trial documents, which are to be held in the local centre (e.g. patients' written consent forms). The principal investigator must ensure the patient's confidentiality is maintained.

ICR-CTSU will maintain the confidentiality of all patients and will not reproduce or disclose any information by which patients could be identified. Representatives of ICR-CTSU and the Radiotherapy QA team will be required to have access to patients notes for quality assurance purposes but patients should be reassured that their confidentiality will be respected at all times. In the case of special problems it is also necessary to have access to the complete study records provided that patient confidentiality is protected.

#### 22.3 Ethical Considerations

This trial has been approved by the South East Coast Kent Research Ethics Committee. Before entering patients, the Principal Investigator at each centre is responsible for gaining Site Specific Assessment and Research and Development approval for this study.

It is the responsibility of the Principal Investigator to give each patient, prior to inclusion in the trial, full and adequate verbal and written information regarding the objective and procedures of the trial and the possible risks involved. Sufficient time (a minimum of 24 hours) should be allowed for the patient to decide on trial entry. Patients must be informed about their right to withdraw from the trial at any time. Written patient information must be given to each patient before enrolment. The written patient information is an approved patient information sheet (PIS) according to national guidelines. There are 2 separate PIS for the trial. One is for the first 150 patients in the trial and details the "Short term side effects" study. A second PIS is to be used for all other patients once 150 patients have been recruited into the study. It contains details of the collection of biological samples, Quality of Life and photographic sub-studies. Patients will be encouraged to participate in these associated studies but if they decline, this will not exclude them from the trial.

All consent forms must be countersigned by the Principal Investigator or a designated individual. A record listing the designated individuals and the circumstances under which they may countersign consent forms must be clearly documented at the centre

as part of the Delegation of Responsibilities Log. This log, together with original copies of all signed patient consent forms, must be available for inspection.

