#### 7. RANDOMISATION

#### 7.1 Randomisation Procedure

An eligibility checklist must be completed and patient consent obtained prior to randomisation.

To randomise a patient, the appropriate centre staff should telephone the ICR-CTSU randomisation line (see below).

Randomisation [contact] Office Hours: 09:00 – 17:00 Monday-Friday

The following information will be required at randomisation:

- name of centre, consultant and person randomising the patient
- patient's full name, hospital number, date of birth, post code and NHS number
- confirmation that an eligibility checklist has been completed and written informed consent has been obtained
- whether the patient has consented to the treatment side effects study (first 150 patients only)
- whether the patient has consented to photographic assessments (once 150 patients have been recruited to the trial)
- whether the patient has consented to take part in the QL study (once 150 patients have been recruited to the trial)
- whether the patient has consented to blood sample and tissue collection

- whether the patient has consented to the use of information held by the NHS and the General Register Office
- whether a boost is to be given and what dose level

The caller will be given the patient's unique randomisation number (Trial ID) and the treatment allocation. The Trial ID together with the patient's initials, date of birth and hospital number should be used on all Case Report Forms (CRFs).

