# 8.2 Treatment-related Endpoints

#### 8.2.1. Acute reactions (first 150 patients in the trial)

Acute reactions of the skin of the treated breast will be recorded in the first 150 patients recruited into the trial. This will be assessed as described below.

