#### 17.4 Interim analyses and Data Monitoring

The Independent Data Monitoring Committee (IDMC) will review the data on early skin reactions (up to 3 months following treatment) after the first evaluable 150 patients. This is based on data from the FAST Trial that has found a proportion of RTOG grade ≥3 acute skin reactions in the test groups (30 Gy and 28.5 Gy) of 2.3% and 10.9% in the control group (50 Gy). For each test group in the FAST-Forward Trial we would like to rule out a proportion of RTOG grade ≥3 acute skin reactions of 10.9% ( $p_0$ =89.1%). We expect this rate to be around 2.3% ( $p_1$ =97.7%) in the test groups (27 Gy and 26 Gy). Using the Simon single stage design (using exact p-values) with power 89.2% and one-sided alpha of 7.9%, 50 patients per group will be required (total 150). In each test group, if 3 or more patients develop grade ≥3 acute skin reactions, the IDMC may advise the Trial Steering Committee (TSC) to consider a change in the test schedule.

Interim analyses of local tumour control, normal tissue responses, radiotherapy side effects and the other endpoints will be conducted at yearly intervals and presented to the IDMC for confidential review. In the light of the interim analyses, the IDMC will advise the TSC if, in their view, the trial has indicated 'proof beyond reasonable doubt' that one of the schedules is clearly indicated or contraindicated in terms of local tumour control and/or normal tissue responses. In reviewing the evidence, the IDMC will also consider any available data from other randomised trials involving similar comparisons. The TSC may then consider modification or termination of the study. Unless such a

situation arises, the Trial Management Group (TMG), the collaborators and the central administrative staff (except the statistician who prepares the analyses) will remain unaware of the interim results. The IDMC may recommend continuation beyond the planned number of patients in the main trial, the Quality of Life study or in the number of patients having photographic assessments, if it is felt that further information is required to address reliably the hypothesis in question.

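### The acute-skin safety rule needs 50 evaluable patients per group, but the entry instructions count 150 recruited patients and allow for no loss

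*Protocol*

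**What the plan says.** **The design.** Section 17.4 sets out to "rule out a proportion of RTOG grade ≥3 acute skin reactions of 10.9" per cent in each test group, and adds "We expect this rate to be around 2.3" per cent. With "power 89.2% and one-sided alpha of 7.9" per cent it concludes that "50 patients per group will be required (total 150"). A test group is flagged at 3 or more grade ≥3 reactions, and the committee may then advise the steering committee to consider changing the schedule. The committee "will review the data on early skin reactions (up to 3 months following treatment) after the first evaluable 150 patients".

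**The entry rule.** Other sections count differently:
- Section 8.2.1: "Acute reactions of the skin of the treated breast will be recorded in the first 150 patients recruited into the trial".
- Section 7.1 lists, among the randomisation questions, "whether the patient has consented to the treatment side effects study (first 150 patients only").
- Section 22.3 describes two information sheets. The first covers the short-term side effects study. On the change of sheet it says: "A second PIS is to be used for all other patients once 150 patients have been recruited into the study".
- Section 9 places the acute assessments in the first 150 patients of the study. Section 18.3 treats the end of the acute study as the moment when 150 have been recruited.
- The sample size entry of the Trial Summary and section 17.3.2 give only an approximate 150.

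Sections 17.3.1 and 17.3.3 allow for up to 10% loss or unevaluable patients in the main trial and the sub-studies. Sections 17.3.2 and 17.4 state no such allowance for the acute study.

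**The concern.** The statistical section counts evaluable patients and the site-facing sections count recruited patients. The two agree only if every one of the first 150 consents to the acute study and is assessed well enough to be graded. Section 7.1 records consent to that study as its own item, so a patient can evidently be randomised without it. A site that follows sections 7.1, 8.2.1 and 22.3 stops asking at 150 recruited and moves to a sheet that is not described as covering the acute study. No route to replace a refusal is then given.

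The flag count is a fixed number, so each lost patient makes the flag less likely at any true rate. What is at stake is the stated 7.9%: the chance that a test group whose true rate is 10.9% raises no flag.

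**Working it through.** **Inputs.** From section 17.4: unacceptable rate 10.9%, expected rate 2.3%, n = 50 per group, flag at 3 or more. From section 7.2: 1:1:1 allocation in permuted blocks, stratified by centre and risk group. The evaluable fraction in the acute study is not stated, so a range of 80% to 100% is assumed.

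**Formula.** The probability of no flag is P(X ≤ 2) = Σ C(n,k) p^k (1−p)^(n−k) over k = 0, 1, 2. At p = 0.109 this is the stated alpha; at p = 0.023 it is the stated power.

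**Reproducing the plan at n = 50.**
- p = 0.109: 0.0031 + 0.0191 + 0.0572 = 0.0794, the stated 7.9%.
- p = 0.023: 0.3124 + 0.3677 + 0.2121 = 0.8922, the stated 89.2%.

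The design is therefore exact for 50 evaluable patients. A search over sample sizes found 50 to be the smallest n with alpha at most 8% and power at least 89%, so it holds no hidden reserve.

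**If entry stops at 150 recruited.** Expected evaluable patients per group = 50 × evaluable fraction, with the flag left at 3:

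| Evaluable fraction | n per group | No flag at true 10.9% | No flag at true 2.3% |
|---|---|---|---|
| 100% | 50 | 7.9% | 89.2% |
| 96% | 48 | 9.3% | 90.2% |
| 90% | 45 | 11.8% | 91.5% |
| 80% | 40 | 17.4% | 93.6% |

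**How easily 50 is missed under that wording.** With exactly 50 allocated to each test group and independent losses, both groups reach 50 evaluable only if none of the 100 patients is lost. That probability is 0.98^100 = 13% at 98% evaluable and 0.95^100 = 0.6% at 95%.

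**Chance imbalance alone.** Stratified blocks will not put exactly 50 in each group even if all 150 are evaluable. The alpha is 9.3% at 48, 8.6% at 49, 7.9% at 50, 7.3% at 51 and 6.7% at 52. That is 0.6 to 0.7 percentage points per patient, in either direction.

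**Entry needed for 150 evaluable.** 150/0.95 = 158; 150/0.90 = 167; 150/0.80 = 188 (rounded up).

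**The case against.** The best defence is that section 17.4, which governs the safety review, already says evaluable, and that the approximate 150 in section 17.3.2 signals a target with some give. On that reading the remaining passages are loose wording and the trial would go on until the committee had its 150. This stands to the extent that closure at 150 recruited is not uniform in the document. It does not remove the conflict: the evaluable count cannot be met if the consent question and the first sheet both end at 150 recruited, and an approximate number gives sites no stopping point.

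The rule is also advisory, and the committee meets at least annually (section 19.3) and sees yearly analyses of side effects. That stands too: a shortfall weakens the rule without disabling safety oversight.

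Three stronger readings are tempting and are not supported:
- **That 50 per test group will usually not be reached.** This needs both the recruited wording and an uptake figure that the protocol does not give. The 10% allowance belongs to the main trial and the sub-studies.
- **That uneven group sizes make the rule unsafe.** With block size 6 and 20 to 40 strata assumed, both test groups reach 50 in only about 23% to 27% of simulated trials, even with everyone evaluable. But imbalance takes groups above 50 as well as below, and moves the alpha little. Only real loss is one-directional.
- **That a missed weekly visit makes a patient non-evaluable.** Skin is graded repeatedly during treatment and for 4 weeks afterwards, and the protocol does not equate one missed visit with non-evaluability.

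Finally, the sentence in section 22.3 about declining follows the description of the second sheet, so optional consent to the acute study rests on section 7.1.

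**Conclusion.** The protocol contradicts itself on who counts towards its numerical early safety rule: evaluable patients in section 17.4, recruited patients in sections 7.1, 8.2.1, 9, 18.3 and 22.3, and an approximate figure in section 17.3.2 and the Trial Summary. The design has no allowance for loss. If the recruited wording is followed, the chance of missing a true 10.9% rate rises from 7.9% to 11.8% at about 45 evaluable per group and to 17.4% at about 40. Those group sizes rest on assumed losses of 10% and 20%. The error is towards missing excess toxicity. The effect is moderate, and it depends on uptake and on which wording sites apply. It should be corrected because the stated error rates hold only at 50 evaluable per group and the correction is cheap.

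**What to change.** Reconcile sections 1, 7.1, 8.2.1, 9, 17.3.2, 17.4, 18.3 and 22.3 on one denominator, evaluable patients. Keep the first information sheet and the side-effects consent question in use beyond 150 recruited, until about 50 evaluable patients per test group are secured, and tie the change to the second sheet and the start of the quality of life and photographic studies to that point. Because evaluability is known only some weeks after radiotherapy, a working entry target is practical: about 158 patients if 95% are expected to be evaluable, 167 if 90%. Give the committee the number evaluable in each test group at its review, with the exact error rates of the existing rule at that number.

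The cost is wording in the protocol and site instructions, weekly skin checks for a few more patients, and a slightly later start to the sub-studies. After 167 patients, 4,000 − 167 = 3,833 remain for sub-studies that need 2,196.
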